#### **Study Time Line and Procedures:**

Patients will receive three in-person evaluations during this study. An outline of the testing that will take place during these visits is provided in **Schedule 1 (attached)**.

#### **Baseline Screening:**

A baseline evaluation will determine the eligibility of each recruited individual to participate in the study. At this visit consent will be obtained, and measurements of height, weight, blood pressure, pulse, urinalysis, and electrocardiogram will be performed. A blood specimen will be drawn for: complete blood count and differential

cell count, serum sodium, chloride, potassium, bicarbonate, calcium, phosphorus, total protein, glucose, blood urea nitrogen, prothrombin time, partial thromboplastin time, creatinine, thyroid stimulating hormone, T3, T4, gamma glutamyl transferase, aspartate aminotransferase, and lactic dehydrogenase. A pregnancy test will be given to women of childbearing potential.

Patients will be required to have had a 24 hour Holter monitor study performed within 2 months, or prior to their initial screening visit. The Holter monitoring assessment will occur through collaboration with our study cardiologist, Dr. [REDACTED], who is reviewing the resting electrocardiograms and 24 hour Holter monitoring results on each of the study participants. Patients will come to the University of Rochester Medical Center > 36 hours before their scheduled Clinical Research Center [CRC] visit for out-patient electrode placement and attachment of the Holter recording equipment. The Holter equipment and electrode removal will occur at the time of admission of the participant to the CRC. Rapid review of the tracing will occur to allow a determination of their eligibility after all the initial baseline screening is performed to assure that the patient satisfies the inclusion and exclusion criteria for participation in the trial of mexiletine. The out of town participants will stay in a hotel close to the University of Rochester Medical Center during the period before their CRC admission. The application of the Holter monitor will occur as noted above as an out-patient procedure that will be coordinated through our cardiology group, including Drs. [REDACTED] and [REDACTED] (cardiologists), [REDACTED] (ECG Core Lab Manager) and [REDACTED] (Technician).

Past medical history will be collected by the study coordinator and a physical exam will be completed by one of the investigators. If an individual patient meets the inclusion criteria and has none of the exclusion criteria, that patient will be enrolled and their inpatient evaluation continued. If recruited individuals do not meet the inclusion criteria or have one or more exclusion criteria, they will not be eligible to participate and will not continue in the study.

### **Screening Evaluations:**

- Review of the study procedures/consent review: Upon arrival at the CRC, the information in the screening consent form will be reviewed with the patient in detail. The patient will be provided with an opportunity to ask any additional questions prior to starting the study procedures scheduled for the day.
- Standard blood testing. Up to 4 tablespoons of blood will be taken from a vein in the participants arm. This blood will be used for routine laboratory testing listed above and in the schedule. A pregnancy test will also be performed for women of childbearing potential.
- A urine sample will be collected a urinalysis will be performed. Height, weight, and vital signs will be recorded.

- A standard 12 lead electrocardiogram (ECG) test will be performed.
- A study doctor will perform a physical examination and medical history. Medical records will be reviewed.
- A 6-minute walk test (6MWT) will be performed under the supervision of a trained physical therapist. Blood pressure, heart rate, breathing rate, and oxygen saturation will be recorded before and after this test.
- A swallowing evaluation will be conducted to determine the ability of the patient to swallow pills with water.
- Myotonia testing. For this testing we will have the patient grasp a handle that is connected to a computer. The patient will squeeze the handle as strongly as they can for 3 seconds and then relax. The time required for the patient's hand to relax will be recorded by the computer and be used to measure the patient's hand myotonia. To find out if repeated muscle contractions shorten the time required for grip to relax (warm-up effect) a similar test will be performed. With the right hand patients will grasp onto the handle. They will squeeze the handle as strongly as they can for 3 seconds and then relax for 10 seconds. They will repeat this five times. This series of grip exercises will be repeated for a total of 3 sets. Each set will be separated by a 10 minute rest period.
- Placement of a 12-lead 24-hour Holter monitor test. The patient will come to the University of Rochester Clinical Research Center (CRC) and a technician from the Cardiology Group working on this project will work with the CRC nursing staff to set up the Holter monitor. Patients will not require this testing if they have had a Holter monitor within 2 months. This testing can be done before or after the above screening procedures and after the screening consent form has been reviewed and signed.

**Potential Enrollment: All screening information will be reviewed by the PI to determine subject eligibility. If a patient satisfies all the inclusion and exclusion criteria, the patient will be invited to participate in the research study and a consent form for the treatment trial (attached) will be reviewed with them. If the patient decides to participate in the clinical trial the patient will undergo the following:**

- I. Continuation of the Screening/Baseline Visit at the University of Rochester Clinical Research Center (CRC). This visit will take two days. During this visit a series of evaluations will be carried out to determine how the patient is affected by myotonic dystrophy. An additional aspect of the Screening/Baseline Visit is that the patient will be started and monitored on the study drug (either mexiletine or placebo).

- II. Follow-up visits to the CRC 3 months and 6 months after the Screening/Baseline Visit. During these visits many of the same evaluations from the Screening/Baseline Visit will be repeated to determine how the patient's condition has changed over time.
- III. Telephone evaluations. The patient will receive a telephone call about every two weeks while they are enrolled in the study, except for the weeks when they come to the CRC for a study visit. The study coordinator will telephone the patient to check on any side effects that may occur and make sure that the study medication is being taken as directed. The coordinator will also ask each patient about their pain level during these phone calls.

A schedule of procedures and assessments for this project is outlined in **schedule 1** (Appendix C).

#### **Description of study procedures:**

The Screening/Baseline Visit of the study will take place over two consecutive days on the CRC. On Day 1 the patient will be admitted to the Clinical Research Center (CRC) for an overnight stay.

Screening/Baseline Visit Day 1 - The activities during the first day will take all day (about 4 hours in the morning and 3 hours in the afternoon). These activities include the screening evaluations listed above as well as the procedures outlined below.

- Review of the study procedures/consent review: Upon arrival at the CRC, the information in the treatment consent form will be reviewed with the patient in detail. The patient will be provided with an opportunity to ask any additional questions they may have prior to starting the study procedures scheduled for the day.
- An assessment of the patient's ability to swallow. A swallowing evaluation will be conducted to determine the time it takes for the patient to swallow water.
- The patient's muscle strength will be tested in several ways by a physical therapist using hand grading and a myometer. The patient's force vital capacity will be checked. The patient will be timed as they get up from a chair and walk 30 feet and perform a Purdue Peg Board test and Jebsen-Taylor Hand function tests. The patient will be asked to pinch a piece of equipment with their fingers to measure their pinch strength.
- Each patient will be given a standard lunch on the CRC.
- They will be asked to complete a series of questionnaires to find out how myotonic dystrophy impacts upon the patient's life and daily activities. These include the following questionnaires: Upper Extremity Functional Index, myotonia visual analog scale, Medical Outcome Short Form Health Survey (SF 36), Epworth Sleepiness Scale, an Individualized Neuromuscular Quality of Life

Questionnaire (INQoL), two gastrointestinal function questionnaires, a chronic pain scale and brief pain inventories, and a DM1 specific Health related quality of life questionnaire (MDHI). Additionally, patients will be asked to complete an assessment of the usability and relevance of some of these questionnaires (i.e., SF-36, INQoL, and MDHI).

- Each patient will receive a standard dinner on the CRC.
- After all of the baseline assessments are completed, each patient will receive the first dose of study medication (mexiletine or placebo) with dinner. The patient will stay overnight on the CRC.

Screening/Baseline Visit Day 2 - The activities during the second day will take approximately 4.5 hours to complete. The procedures described for Day 2 will begin on the Clinical Research Center (CRC) in the morning at 7:30AM.

- Each patient will be given a second dose of study medication with their breakfast. The amount of muscle tissue, fat tissue, and bone in the body will be measured using dual energy X-ray absorptiometry (DEXA). The DEXA machine will scan over the patient's body while they lie still for about 15 minutes. The DEXA scan involves radiation exposure which is less than one day's worth of exposure to natural background radiation.
- Video-recording of Hand Opening Time. The dominant wrist and hand are placed on a bedside table with the forearm fully supinated. The participant is asked to open the hand after making a tight fist for 3-5 seconds. A digital video recording is made of the hand opening. The video field of view only includes the participant's forearm and hand. The time required for hand opening, which often ranges from 3 to 20 seconds in individuals with DM1, is determined by blinded review of the video recording. The procedure is carried out three times over 30 minutes.
- Each patient will be given a third dose of study medication with their lunch.
- Up to 4 tablespoons of blood will be taken from a vein in the patient's arm. This blood will be used for routine laboratory testing listed in the schedule. The level of mexiletine in the blood will also be measured.
- An electrocardiogram will be performed and reviewed by a physician in real-time.
- The study coordinator will give each patient bottles containing a three month supply of study medication. Each patient will also be given a diary to record the amount of medication taken each day and any side effects that they may experience. The coordinator will go over instructions for taking the study medication and completing the medication diaries. At the 3 and 6 months follow-up visits patients will be asked to return the study medication bottles, any unused study medication, and completed diaries.

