**Diet:**

During inpatient evaluations on the Clinical Research Center of the University of Rochester Medical Center (CRC) each participant will receive a constant diet that is designed in advance with the CRC dietitian. The meals provided on Study Day 1 will be the identical to the meals provided on Study Day 2. Each meal will be given at the same time (8AM, 12:30PM, and 6:00PM) on both Study Days 1 and 2. During both study days participants will only consume the research diet provided and will not perform vigorous physical exertion other than that required for the muscle strength testing in the research protocol. This dietary control helps to avoid changes in hormonal regulation of potassium balance that might exert a significant influence on the degree of myotonia in study participants.

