**Randomization:**

After eligibility has been confirmed and the treatment consent has been reviewed and signed, the patient will be randomized to one of two treatments (placebo or mexiletine) according to the randomization plan developed by the biostatistics programmer at the University of Rochester, under the supervision of the biostatistician (Dr. [REDACTED]). The randomization will include blocking to insure balance among the two treatment sequences after a certain number of patients have been enrolled. Only Dr. [REDACTED] and the biostatistics programmer will be aware of the block size used.

After the randomization plan has been generated by the biostatistics programmer, it will be sent to the pharmacy at the University of Rochester Medical Center where drug packaging and labeling will take place. All drug will be labeled with a patient ID number. Only the biostatistics programmer and the pharmacist will have access to the treatment assignments, i.e., the link between the patient ID number and treatment. The biostatistician (Dr. [REDACTED]) will remain blinded to treatment assignment.

Drug will be assigned sequentially. No patient will be dispensed study drug until after all baseline assessments have been completed. The study coordinator will be required to check all baseline forms for completeness and verify eligibility criteria before calling the pharmacy to officially randomize a patient. Enrollment will be documented on a case report form.

The biostatistics programmer will also provide the study coordinator with a set of sealed emergency disclosure envelopes which will allow the investigator to become quickly unblinded to the patient's treatment assignment in case of a medical emergency. It is anticipated that such disclosure will not be necessary in this study.

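### The only baseline video of hand opening that the protocol describes is made on Day 2, after study drug has started, against the plan's own rule that baseline assessments come first

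*Combined protocol and SAP*

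**What the plan says.** Two sections set the same rule. Description of study procedures (Day 1) says: "After all of the baseline assessments are completed, each patient will receive the first dose of study medication (mexiletine or placebo) with dinner". Randomization says: "No patient will be dispensed study drug until after all baseline assessments have been completed".

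The Day 2 list under Description of study procedures opens with "Each patient will be given a second dose of study medication with their breakfast" and then, before the lunch dose, gives "Video-recording of Hand Opening Time. The dominant wrist and hand are placed on a bedside table with the forearm fully supinated". The test is done three times over 30 minutes and read by blinded review.

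The Diet section fixes the clock: "Each meal will be given at the same time (8AM, 12:30PM, and 6:00PM) on both Study Days 1 and 2". Day 2 procedures begin at 7:30AM.

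The baseline myotonia test under Screening Evaluations is the grip test: "For this testing we will have the patient grasp a handle that is connected to a computer". Neither that section nor the Day 1 list mentions the video. The Evaluation of Myotonia section makes the video one of two serial myotonia procedures and ranks grip relaxation time above it. The protocol also refers to a timetable that is not in the text available here: "A schedule of procedures and assessments for this project is outlined in" Schedule 1 (Appendix C).

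**The concern.** If the Day 2 list is followed as written, the value that serves as baseline for hand-opening time is taken on study drug. Months 3 and 6 are also on treatment, so no off-drug recording would exist for any participant, and one cannot be obtained after dosing has begun.

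The section on secondary efficacy outcomes adjusts each outcome for its baseline value in a repeated measures analysis of covariance. A baseline that already carries some drug effect removes part of that effect from the adjusted difference. The video could then appear to disagree with grip relaxation time only because the two baselines were taken at different times relative to dosing. If an early effect were present on Day 2 and gone by Month 6, the adjusted difference would be biased against mexiletine.

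**Working it through.** **Sequence**

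- First dose: Day 1 dinner, 6:00PM. Second dose: Day 2 breakfast, 8AM. Third dose: Day 2 lunch, 12:30PM.
- Earliest possible Day 2 recording: 7:30AM. From 6:00PM this is 6 h to midnight + 7.5 h = 13.5 h after the first dose. The recording is post-dose even if made before breakfast.
- If the listed order is followed (between breakfast and lunch), it falls 14 to 18.5 h after the first dose and 0 to 4.5 h after the second.
- The later description of the method, under Evaluation of Myotonia, gives no timing, so nothing visible places a recording before the first dose.

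**Size of any bias**

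The plan gives no figure for this measure to reproduce. Let T be the true Month 6 effect, D the effect present at the Day 2 recording, and b the slope on baseline. All three are assumptions.

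The observed baseline difference between arms is D in expectation, so:

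expected adjusted difference = T − b × D

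If D = f × T, the share of the true effect kept is 1 − b × f:

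| f | b = 0.5 | b = 0.7 | b = 0.9 | b = 1 (change score) |
|---|---|---|---|---|
| 0 | 100% | 100% | 100% | 100% |
| 0.10 | 95% | 93% | 91% | 90% |
| 0.25 | 87.5% | 82.5% | 77.5% | 75% |
| 0.50 | 75% | 65% | 55% | 50% |

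A simulation with 20 per arm and unit standard deviations at both times (20,000 runs per cell) agrees. For example, at f = 0.25 the shares are 0.874, 0.827 and 0.777 for b = 0.5, 0.7 and 0.9.

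**Early effect that has faded (T = 0)**

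The expected difference is −b × D, which is against mexiletine. If that bias equals k standard errors, two-sided rejection at a nominal 5% is:

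| k | Noncentral t, 37 df | Simulation, b = 0.5 / 0.7 / 0.9 |
|---|---|---|
| 0.5 | 7.8% | 7.6 / 7.6 / 7.9% |
| 1.0 | 16.4% | 15.4 / 15.4 / 16.0% |
| 1.5 | 30.9% | 26.7 / 29.1 / 30.0% |

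With T = D = 0 the simulation rejects 5.0% to 5.2% of the time.

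To give k = 1 a scale: with equal unit standard deviations the standard error is √(2/20) × √(1 − b²), which is 0.274, 0.226 and 0.138 for b = 0.5, 0.7 and 0.9. Dividing by b, the Day 2 effect needed is 0.55, 0.32 and 0.15 baseline standard deviations.

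**Room on Day 1**

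The protocol states: "The activities during the first day will take all day (about 4 hours in the morning and 3 hours in the afternoon". Lunch at 12:30PM to dinner at 6:00PM is 5.5 h; 5.5 − 3 = 2.5 h, less the meal itself. The test takes 30 minutes.

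**The case against.** The strongest reply is that no harmed analysis is actually specified. The Secondary Aims, the outcome list under Trial Design and the list of secondary efficacy variables all omit video hand opening. The nearest item, a rapid hand contraction and extension time, may be a different task. The follow-up itinerary does not name the video either. Schedule 1 may place the recording correctly, and the coordinator must check that baseline forms are complete before the pharmacy is called, so the Day 2 entry may be only a misplaced bullet.

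Much of this stands. Use of the Day 2 value as a covariate is an inference, and the confidence here covers the written sequence, not what staff would do. But the Evaluation of Myotonia section does present the video as a serial efficacy procedure, and the Day 2 list needs correcting even if Schedule 1 is right.

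It is also fair that every input to the bias calculation is assumed, and that rejection rates for a bias stated in standard errors would hold in any trial. The faded-effect case is remote: the plan reports benefit after seven weeks in its earlier trials and no loss of efficacy over years in non-dystrophic patients. Its extra rejections would count against mexiletine, so it would not produce a false claim of benefit. The seven-week result, however, shows when benefit was measured, not when it began, so an early effect cannot be excluded.

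Finally, Day 1 must also hold eligibility review, treatment consent, Holter review and randomization, for which no times are given. The spare time is therefore apparent, not proven.

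**Conclusion.** The concern holds. The Day 2 list contradicts the rule stated under Day 1 and under Randomization, and the visible text describes no off-drug video recording. This is certain for the text available, subject to Schedule 1.

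The consequence is conditional and cannot be sized from the documents. It is zero if there is no drug effect by Day 2. Over the assumed range f = 0.10 to 0.50 and b = 0.5 to 0.9, between 95% and 55% of the true effect would be kept. No power loss can be quoted, and these figures are not a forecast.

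Bias from the video timing is confined to that measure. The six-minute walk and grip relaxation time are tested before the first dose. The baseline DEXA scan is also listed on Day 2 and has the same formal conflict. A material change in lean mass within about a day is unlikely, though the documents do not address it.

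**What to change.** 1. Make the baseline video recording on Day 1 before the first dose, leaving dosing times unchanged.
2. Because repeated contractions may shorten relaxation (the warm-up effect that the grip protocol is designed to measure), fix the order of the video and grip tests and a rest interval between them. Use the same order and interval at Months 3 and 6.
3. Label any Day 2 recording as on-treatment and do not use it as the baseline covariate.
4. In the section on secondary efficacy outcomes, state whether video hand opening is a secondary outcome and which recording is its baseline.
5. Reconcile the Day 1 list, the Day 2 list, the Randomization section and Schedule 1, with wording that also settles the timing of the baseline DEXA.

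The cost is resequencing one existing 30-minute test within the same two-day stay, with no new procedure. Day 1 becomes slightly longer, including the rest interval, and the investigators should confirm that it fits alongside eligibility review and consent.

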### **Itinerary of Follow-up Visits: (Month 3 and Month 6)**

The evaluations of patients at their Month 3 and Month 6 Visits will be similar to those performed at their Screening/Baseline Visit with the exception that a DEXA scan will only be performed at Screening/Baseline and at Month 6. Holter monitoring will occur within the week immediately before the CRC admissions at Month 3 and Month 6, and the procedure for placement of the Holter recording equipment and electrode placement will use the same standard procedure described above and routinely used by our cardiology consultant group at the University of Rochester Medical Center.

On the Month 3 and Month 6 follow-up visits, the patient will complete the following study procedures following an overnight fast. The patient will be supplied with a standard breakfast after the blood draw.

- An electrocardiogram will be performed.
- The patient will have up to 4 tablespoons of blood drawn, and if the patient is a female of childbearing potential, a pregnancy test will be done. A urine sample will be collected to test kidney function.
- A study doctor will perform a history and physical examination; height, weight and vitals will be recorded.
- A study doctor and study coordinator will discuss any side effects that the patient may have experienced and any recent changes in medications.
- An assessment of the 6-minute walk test (6MWT) will be performed.
- A swallowing evaluation will be conducted.
- Myotonia, functional, and strength testing will be performed (as described above).
- A standard lunch will be given on the CRC.
- A DEXA study will be performed (six month only).
- Questionnaires will be completed (Upper Extremity Functional Index, myotonia visual analog scale, Medical Outcome Short Form Health Survey (SF 36), Epworth Sleepiness Scale, an Individualized Neuromuscular Quality of Life Questionnaire (INQoL), two gastrointestinal function questionnaires, chronic pain scale and brief pain inventories, and a DM1 specific Health related quality of life questionnaire (MDHI). Additionally, patients will be asked to complete an assessment of the usability and relevance of some of these questionnaires (i.e., SF-36, INQoL, and MDHI).
- The study coordinator will collect medication bottles, unused medication and the patient's diary. At the month 3 visit, the patient will be provided with a new supply of study medication and a patient diary.
- The patient will receive a standard dinner on the CRC.

Once all of these activities are completed, the visit will be finished and the patient will be discharged from the CRC.

